#### **9.4.1 Description of Subgroups to be Analyzed**

The following subgroups will be explored for the primary and key secondary endpoints:

1. Age (<65, ≥65)
2. Sex (male, female)
3. Race (Caucasian, African, Asian, Other)
4. Weight (<80 kg versus. ≥80 kg)
5. Participants with prior surgery
6. Participants with comorbid asthma (including AERD).
7. Region (North America, Europe, rest of world)

Other possible subgroup analyses will be presented in the SAP.

#### **9.5 Statistical Analysis Methodology**

Statistical analysis will be performed using SAS software Version 9.4 or later. Continuous variables will be summarized using the mean, SD, median, minimum value, and maximum

value. Categorical variables will be summarized using frequency counts and percentages. Data will be listed in data listings. All confidence intervals (CIs) presented will be 99% (2-sided) CIs for primary and key secondary endpoints.

Full details of the statistical analyses, methods, and data conventions will be described in the SAP.

### **9.5.1 General Considerations**

Data collected in this study will be presented using summary tables, participant data listings and figures. For continuous variables, the number of observations, mean, SD, median, minimum, and maximum will be presented. Categorical variables will be summarized by participant counts and percentages. For ordinal-scaled variables, a combination of presentations may be employed as appropriate: frequency and percentage of observations within a category and means and SDs of the scores of the categories. For categorical and ordinal variables, percentages will be calculated based on the N of the analysis set and number of participants with missing data will also be included. For the efficacy and safety analysis during the induction period, the 2 lebrikizumab arms will be pooled and thus there will be 2 treatment groups. Treatment comparisons for the induction period will be made between lebrikizumab Q2W (pooled) versus PBO.

### **9.5.2 Overview of Statistical Methods: Estimation of Estimands**

The primary estimand is a hybrid estimand representing the primary clinical question of interest: what is the difference in means between treatment conditions (lebrikizumab versus PBO), in the target participant population, with NP surgery, change to another approved biologic therapy or long-term use of SCS or nasal saline lavage with corticosteroids considered as treatment failure, regardless of study treatment discontinuation or short-term use of SCS?

[Table 9-3](#) presents a summary of primary statistical methods. Details pertaining to any planned sensitivity and supplementary analyses will be specified in the SAP.

**Table 9-3 Summary of Primary Statistical Methods**

Estimand Label	Estimand Description	Main Estimation		
		Analysis Set	Censoring Rules	Analysis Model/Method
Primary Estimand	The difference in means in change from baseline compared between participants treated with lebrikizumab and PBO in combination with background INCS, regardless of treatment discontinuation or short-term use of SCS treatment. Short-term use of SCS is defined as ≤1 mg/kg prednisone equivalent per day for less than and equal to 7 days of use. Nasal polyp surgery, change to another approved biologic therapy, or long-term use of SCS or nasal saline lavage with corticosteroids will be considered as treatment failures. In the case of treatment failure, values will be replaced with the worst possible scores.	ITT	Data collected after treatment discontinuation or short-term use of SCS will be included in the analysis.  For participants who undergo nasal polyp surgery or change to another biologic therapy or use long-term SCS or nasal saline lavage with corticosteroids, data collected after ICEs will be set to missing and imputed by the worst possible scores.  The remaining missing data will be imputed under missing at random assumption (multiple imputation).	ANCOVA with the following covariates in the model: treatment group, baseline value, and stratification factors. Type III tests for LS means will be used for statistical comparison between treatment groups.

Abbreviations: ANCOVA = analysis of covariance; INCS = intranasal corticosteroid; ICE = intercurrent event; ITT = intent-to-treat; LS = least squares; PBO = placebo; SCS = systemic corticosteroids.

### 9.5.3 Analysis of Co-Primary Efficacy Endpoints

#### 9.5.3.1 Main Estimation of Co-Primary Endpoints

Refer to [Table 9-3](#) for main estimation of the primary estimands for endoscopic NPS and NCS severity.

#### 9.5.3.2 Sensitivity and Supplementary Analysis for Co-Primary Endpoints

Details pertaining to any planned sensitivity and supplementary analysis will be specified in the SAP.

#### 9.5.3.3 Analysis for Supportive Estimands

Details pertaining to any planned supportive estimand will be specified in the SAP.

### **9.5.4 Analysis of Key Secondary Efficacy Endpoints**

For assessments of key secondary efficacy endpoints, treatment comparisons will be made using analysis of covariance with the following in the model: treatment group, baseline value, and stratification factors. Type III tests for least squares (LS) means will be used for statistical comparison between treatment groups. The LS mean difference, standard error, *P* value, and 99% CI, unless otherwise specified, will also be reported.

Proportion of and time-to-event for participants receiving SCS, approved biologics for CRSwNP rescue use, or planned surgery of NP during study treatment period will be derived and analyzed using the Cox proportional hazards model and log-rank test stratified by stratification factors, by considering the first rescue event (defined as any SCS use, approved biologics for CRSwNP, or surgery [actual or planned] for NP) as the event of interest. The estimates of the hazard ratio and corresponding 99% CI will be provided for lebrikizumab Q2W/Q4W Arm versus PBO and lebrikizumab Q2W/Q8W Arm versus PBO.

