**Table 3-1 Objectives and Endpoints**

Objectives	Endpoints
Primary:	

 
To evaluate the efficacy of lebrikizumab 250 mg Q2W compared to PBO in reducing nasal congestion severity and endoscopic NPS on background INCS at Week 24
 
	
 
Mean CFBL at Week 24 in participant reported NCS severity
 
Mean CFBL at Week 24 in endoscopic NPS
 

Key Secondary:	

 
To evaluate the efficacy of lebrikizumab in reducing the signs and symptoms in participants
 
	
 
Mean CFBL at Week 56 in endoscopic NPS
 
Mean CFBL at Week 56 in participant reported NCS
 
Mean change in opacification of sinuses measured by the LMK from baseline to Weeks 24 and 56
 
Mean change in FEV1 from baseline to Weeks 24 in patients with asthma at baseline
 
Mean CFBL in severity of loss of smell at Weeks 4, 24, and 56
 
Mean CFBL in postnasal drip at Weeks 24 and 56
 
Proportion of and time-to-event for participants receiving systemic corticosteroids, and/or approved biologics for CRSwNP rescue use, and/or planned surgery of NP during study treatment period
 

Other Secondary:	

 
To compare the efficacy of lebrikizumab, compared to PBO, as measured by clinician assessments, and as assessed by PROs and quality of life measures in participants
 
	
 
Mean changes in the following from baseline by visit:               
 
Participant reported NCS severity
 
Endoscopic NPS
 
Opacification of sinuses measured by the LMK
 
Severity of loss of smell as assessed by participant daily eDiary score
 
Postnasal drip assessed by participant daily eDiary score
 
FEV1
 
Severity of loss of taste as assessed by participant daily eDiary score
 
Severity of facial pain/pressure as assessed
 
 
 

Objectives	Endpoints

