## 4 Study Design

### 4.1 Overall Design

This is a Phase 3, multinational, multicenter, double-blind, PBO-controlled, parallel group, randomized clinical study to evaluate the efficacy and safety of lebrikizumab in approximately 510 adult participants (≥18 years of age) with CRS and bilateral NP who receive background therapy with INCS. Enrollment will also be open to adolescents at least 12 years of age and weighing at least 40 kg. Any adolescent participant enrolled will not contribute to the target number of 510 participants.

This study has 4 study periods:

- Screening (up to 30 days)
- Run-in (4 weeks)
- Randomized treatment (56 weeks), which includes an induction period (24 weeks; Week 0 to Week 24) and a maintenance period (32 weeks; Week 24 to Week 56)

- Safety follow-up (SFU; 8 weeks), starting after the study site visit at Week 56. For participants who complete the final maintenance visit at Week 56, SFU (Visit 801) will occur at Week 64 (12 weeks after the last dose scheduled at Week 52). If a participant withdraws from the study early, SFU (Visit 801) will be scheduled to occur 12 weeks after the last dose received.

The maximum planned duration of study participation for each participant will be up to approximately 72 weeks.

Adult participants meeting the inclusion and exclusion criteria ([Section 5.1](#) and [Section 5.2](#), respectively) will be randomly assigned 1:1:1 to the following treatment arms at baseline (Visit 3) (see [Table 6-2](#) and [Table 6-3](#) for dosing details):

- Lebrikizumab Q2W/Q4W Arm: Lebrikizumab 500 mg loading dose at Week 0 and Week 2, followed by lebrikizumab 250 mg Q2W through Week 24 (induction period) and then lebrikizumab 250 mg Q4W through Week 56 (maintenance period).
- Lebrikizumab Q2W/Q8W Arm: Lebrikizumab 500 mg loading dose at Week 0 and Week 2, followed by lebrikizumab 250 mg Q2W through Week 24 (induction period) and then lebrikizumab 250 mg Q8W through Week 56 (maintenance period).
- PBO Arm: PBO Q2W through Week 24 (induction period) and then PBO Q4W through Week 56 (maintenance period).

Randomization for adult participants will use block randomization with fixed block size and will be stratified by the following factors:

- Asthma and/or aspirin-exacerbated respiratory disease (AERD) versus no asthma/no AERD
- Prior NP surgery versus no prior NP surgery
- Geographic region (North America, Europe, rest of the world)

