#### **8.2.4 Spirometry**

Spirometry is used to measure the physiologic air flow during FEV1.

Spirometry will be performed in all participants at screening (Visit 1) after withholding the last dose of short-acting bronchodilator for at least 6 hours, using a study-supplied spirometer that meets the American Thoracic Society/European Respiratory Society recommendations. At subsequent visits, spirometry will be performed for only participants with asthma according to the SoA ([Table 1-1](#)). Normal FEV1 values are typically  $\geq 80\%$  ([Barriero and Perillo 2004](#)). Lower FEV1 values can indicate more severe asthma or other causes of airway restriction or obstruction. Spirometry will be conducted by trained and qualified personnel, according to procedures specified in the study reference manual.

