### **8.3.4 Height**

Height will be measured at screening and recorded to 1 decimal place without rounding. The instruments used for measuring height should be appropriately and regularly calibrated. Height for adolescents will also be measured whenever vital signs and weight are assessed

according to the SoA (Table 1-1) to evaluate participants' growth over time.

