## 9.3 Sample Size Determination

The planned sample size for adults is approximately 510 participants, with 170 participants in the PBO group and 340 participants across the 2 lebrikizumab dose groups. The adult sample size was determined to enable an adequate characterization of the differences in efficacy between lebrikizumab 250 mg Q2W and PBO with regard to mean changes from baseline in NCS severity and endoscopic NPS at Week 24. This planned sample size was calculated based on the treatment effect observed in SINUS-24 and SINUS-52 ([Bachert et al 2019](#)) and uses the assumption that the mean difference in CFBL in NCS severity between lebrikizumab and PBO is 0.62 with common standard deviation (SD) 1.0, and the mean difference in CFBL in endoscopic NPS is 1.48 with common SD 2.1. Assuming normal distribution and no negative correlation between the 2 endpoints and 20% dropout rate, a sample size of 170 participants per arm is expected to be sufficient to provide a combined power of 99% using a 2-sided t-test with alpha of 0.01 for changes from baseline in NCS severity and endoscopic NPS at Week 24. In addition to the co-primary endpoints, the sample size also allows sufficient power for the key secondary endpoint of time-to-event for participants

receiving systemic corticosteroids, and/or approved biologics for CRSwNP rescue use, and/or planned surgery. Assuming the probability of having such rescue events during study treatment period is 27% in the placebo group, and is 10% in the lebrikizumab group, with 170 patients per arm, the study will have approximately 90% power to detect a hazard ratio of 0.35 between the treatment groups using a 2-sided log-rank test with alpha of 0.01. The sample size was calculated using nQuery Version 9.1.

Approximately 1020 adult participants will be screened to achieve 510 randomly assigned to IP. The study will use block randomization with fixed block size and be stratified based on 3 factors: asthma and/or AERD versus no asthma/no AERD, prior NP surgery versus no prior NP surgery, geographic region (North America, Europe, rest of the world). Adult participants without asthma and/or AERD history will be limited to approximately 255 participants (out of the total 510 randomized participants). Adult participants without prior surgery will be limited to approximately 255 participants (out of the total 510 randomized participants). Adult participants may fall in more than one category without limitation in numbers.

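### The Week 24 FEV1 model in Section 9.5.4 leaves out age, sex and height; the test is valid as written, but prespecifying them is a cheap, modest gain in precision

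*Protocol*

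**What the plan says.** Section 9.5.4 gives one model for the key secondary endpoints: "treatment comparisons will be made using analysis of covariance with the following in the model: treatment group, baseline value, and stratification factors". Only the rescue endpoint (proportion and time to event) gets a separate method there.

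Table 3-1 lists, as key secondary, the mean change in FEV1 "from baseline to Weeks 24 in patients with asthma at baseline". Section 8.2.4 matches this: "At subsequent visits, spirometry will be performed for only participants with asthma according to the SoA".

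The first stratification factor in Section 4.1 is "Asthma and/or aspirin-exacerbated respiratory disease (AERD) versus no asthma/no AERD". The other two are prior NP surgery (two levels) and region (three levels).

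Age and sex are collected as demographics (Section 8.1.2). On height, Section 8.3.4 says: "Height will be measured at screening and recorded to 1 decimal place without rounding". Exclusion criterion 29 in Section 5.2 judges FEV1 as a percentage of predicted normal.

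**The concern.** A covariate list written for nasal scores has been carried over to a lung-function endpoint. Two things follow.

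- **Missing covariates.** Baseline FEV1 in litres does not distinguish a small person with normal lungs from a large person with impaired lungs. If room to improve depends on impairment relative to predicted normal, then age, sex and height explain variance that baseline FEV1 alone leaves in the error term. The protocol does not say how predicted normal is computed; that it depends on these three variables is taken here as general knowledge.
- **A constant factor.** Every participant with asthma belongs to the same level of the asthma/AERD factor, so the model names an adjustment that cannot take place.

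At stake is the precision of one key secondary test within a family controlled at two-sided 0.01 (Section 9.8). Neither point puts its validity in question.

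**Working it through.** The protocol gives no FEV1 effect size, SD or power, so it has no figure of its own to reproduce here.

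**Subset size.** Section 9.3 caps participants without asthma/AERD at about 255 of 510. The asthma/AERD stratum therefore has at least about 510 − 255 = 255. The number with asthma is not stated; I assume 255. With 1:1:1 allocation and the lebrikizumab arms pooled for the induction period (Section 9.5.1), that is 85 placebo versus 170 lebrikizumab.

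**Scale of the test.** Detectable difference in SD units = (z for two-sided 0.01 + z for power) × √(1/85 + 1/170). At 80% power this is (2.576 + 0.842) × 0.1328 = 0.45 SD. With 20% dropout (68 versus 136) it is 0.51 SD. This assumes the full 0.01 is available to FEV1; the testing graph is not shown.

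**The constant factor.** I fitted the ANCOVA to simulated data (N = 255; treatment, baseline FEV1, surgery, region) with and without a constant asthma column. Both times the design rank was 6, the treatment estimate 0.1638 and its standard error 0.0505. The intercept absorbs the column, so no degree of freedom is spent.

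**Adding age, sex and height.** None of these inputs is in the documents; all are assumptions:
- predicted FEV1 linear in age, sex and height;
- baseline percent predicted normal with mean 82, SD 15;
- SD of change 0.40 L (this scales out of a percentage reduction);
- a negative correlation between FEV1 change and baseline percent predicted, of size 0.15 to 0.40.

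In a simulated cohort of 400,000, let v be the proportional fall in residual variance when the three covariates join baseline FEV1.
- SE reduction = 1 − √(1 − v).
- Equivalent extra participants = 255/(1 − v) − 255.
- Degrees-of-freedom cost: residual df go from 255 − 6 = 249 to 246, and √(249/246) = 1.006, or about 0.6% on the SE.
- Net SE reduction = 1 − √((1 − v) × 249/246).

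| Correlation (size) | v | SE reduction | Extra participants | Net SE reduction |
|---|---|---|---|---|
| 0.15 | 1.3% | 0.7% | 3 | under 0.1% |
| 0.20 | 2.3% | 1.2% | 6 | 0.6% |
| 0.30 | 5.2% | 2.6% | 14 | 2.0% |
| 0.40 | 9.5% | 4.9% | 27 | 4.3% |

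Two other linear prediction equations gave v from 1.0% to 8.9% over the same correlations. At v = 1.0% the net change is a loss of about 0.1%. With zero correlation nothing is gained and the 0.6% cost remains.

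**In terms of power.** For a test with 80% power at two-sided 0.01, a variance reduction of 1%, 2%, 5% or 10% gives 80.5%, 81.0%, 82.4% or 84.8%, before the degrees-of-freedom cost.

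**The case against.** The strongest reply is that nothing here is an error. Omitting prognostic covariates from a randomized comparison causes neither bias nor type I error inflation, baseline FEV1 is already in the model, and the benefit above comes from a correlation that I assumed. Exclusion 29 is an eligibility threshold; it does not show that percent predicted drives response. Endpoint-specific covariates can also go in the SAP, since Section 9.5 leaves full details there. Most of this stands, and it limits the point to an optional improvement of uncertain size.

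The SAP argument stands only in part. Section 9.5.4 does not defer the covariate list but states it, and under Section 9 a different FEV1 model would have to be documented in the SAP as a change from the protocol.

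Three stronger readings are tempting, and the documents do not support them:
- **That the FEV1 test is flawed or biased.** It is valid as printed.
- **That the constant asthma factor wastes a degree of freedom.** The check shows no effect. The column would vary only if some participants with asthma were entered in the wrong stratum, and it would then model those entry errors.
- **That FEV1 is among the least precisely estimated key secondary endpoints.** No FEV1 variance or effect is given, the asthma share is known only through the cap in Section 9.3, and the alpha reaching FEV1 cannot be read from the text.

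**Conclusion.** The point holds as a minor efficiency improvement. Section 9.5.4 fixes a covariate list that omits age, sex and height for the one key secondary endpoint where they have an evident role, although the trial records all three.

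The size is modest and rests on assumptions: about 1% to 9% of residual variance and 0.5% to 5% of the standard error at correlations of 0.15 to 0.40, less about 0.6% for three degrees of freedom. At or below 0.15 there is little or no net gain. The subset of 255 is also assumed; a larger one makes the degrees-of-freedom cost smaller. Removing the asthma/AERD factor from this model changes no result and only makes the text clearer.

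**What to change.** Add one sentence to Section 9.5.4: *For change in FEV1 at Week 24, the model contains treatment group, baseline FEV1, age, sex, height, prior NP surgery and region; the asthma/AERD factor is omitted because it does not vary among participants with asthma.* If it goes in the SAP instead, record it there as a change from the protocol, before unblinding.

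The cost is that sentence and three degrees of freedom. No new data are needed.

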### **9.5.5 Analysis of Other Secondary Efficacy Endpoints**

The primary efficacy endpoint will be complemented by a wide range of descriptive efficacy analyses. For the other secondary endpoints, all results will be interpreted descriptively for the treatment groups and for each study visit time point (if applicable). Results from the comparative analysis along with CI will be reported. Details of the analysis of other secondary efficacy endpoints will be described in the SAP.

### **9.5.6 Analyses of Exploratory Efficacy Endpoints**

Analyses of exploratory efficacy endpoints will be specified in the SAP.

### **9.5.7 Pharmacokinetic Analyses**

Lebrikizumab PK data will be summarized using descriptive statistics.

Data from this study may be combined with data from other studies to better characterize the PK of lebrikizumab, as well as to explore the relationship between exposure and efficacy and/or safety outcomes. In this case, a separate PK analysis plan will be developed, and the results of these analyses will be described in a separate PK report.

### **9.5.8 Evaluation of Immunogenicity**

The frequency and percentage of participants with preexisting ADA and with TE ADA against lebrikizumab may be reported.

TE ADA are defined as:

- Treatment-induced ADA: those with a titer 2-fold (1 dilution) greater than the minimum required dilution if no ADA were detected at baseline, or
- Treatment-boosted ADA: those with a 4-fold (2 dilutions) increase in titer compared to baseline if ADA were detected at baseline.

For the TE ADA+ participants, the distribution of maximum titers may be reported.

The frequency of neutralizing antibodies against lebrikizumab, if performed, may be reported in TE ADA+ participants.

The relationship between the presence of antibodies and the PK parameters and PD response including safety and efficacy to lebrikizumab may be assessed.

Additional details may be provided in the SAP.

### **9.5.9 Safety Analyses**

All the safety analysis will be based on the SAF Analysis Set.

AEs will be coded using MedDRA. The number and percentage of participants reporting TEAEs, treatment-emergent SAEs including deaths, TEAEs considered related to study treatment, and TEAEs leading to discontinuation from IP will be tabulated by treatment group, system organ class (SOC) and preferred term. The TEAEs by maximum severity and relationship will also be tabulated by treatment group, SOC, and preferred term. AEs, SAEs, deaths, and AEs leading to discontinuation will be listed by participant.

Descriptive statistics for laboratory test results (hematology, clinical chemistry, and urinalysis) will be provided for the observed values and changes from baseline at each scheduled visit. A shift table (abnormal low/normal/abnormal high) will be provided for select laboratory tests.

Descriptive statistics by treatment group will be provided for the observed values and CFBL at each scheduled visit with vital signs assessment.

Results of the physical examinations will be summarized by visit using appropriate descriptive statistics.

